6.3 Modification in Dose or Schedule for Treatment Response

Once AML patients achieve morphologic complete remission with incomplete blood count recovery (CRi) or MDS patients achieve a marrow complete response (Marrow CR) as defined in Section 9.0, decitabine administration may be decreased to 20 mg/m²/day for ten consecutive days, and the cycles may be administered every 6 weeks to limit myelosuppressive toxicity, at the discretion of the treating physician. After two cycles at six week intervals, the dose may be reduced to 20 mg/m²/day for five consecutive days of treatment in six week intervals. If the patient meets the definition of CR with complete cytogenetic response as defined in Section 9.0, administration may further be decreased to three consecutive days per cycle at the discretion of the treating physician.

7.0 PHARMACEUTICAL INFORMATION

7.1 Decitabine

[REDACTED]

[REDACTED]

[REDACTED]

[REDACTED]

[REDACTED]

[REDACTED]

[REDACTED]

8.0 CORRELATIVE STUDIES SAMPLE COLLECTIONS

Bone marrow samples will be collected pre-study, on Cycle 1 Day 10 ± 1 , and on Day 28 ± 4 of Cycle 1, 2, 4, and 6 for correlative studies. Following Cycle 6, bone marrow biopsies should be performed at the discretion of the treating physician to assess for relapse or progression. The bone marrow samples will be collected under HRPO# 201011766 (“Tissue Acquisition for Analysis of Genetic Progression Factors in Hematologic Diseases”) that all patients will be concurrently enrolled in.

Skin biopsy sample will be collected as part of the patient’s participation in HRPO# 201011766 (“Tissue Acquisition for Analysis of Genetic Progression Factors in Hematologic Malignancies”). There is no required time frame for this sample, and it may have been collected months or even years prior to the first dose of decitabine.

9.0 EFFICACY, SAFETY AND CORRELATIVE STUDY MEASURES

A secondary endpoint of this study is to estimate morphologic complete remission rate.

9.1 Response Criteria - AML

AML Patients will be assessed for response according to the IWG criteria:¹

Morphologic complete remission (CR) – Defined as morphologic leukemia-free state, defined as less than 5% blasts in aspirate with marrow spicules and a count of ≥ 200 nucleated cells and no blasts with Auer rods or any persistence of extramedullary disease. When erythroid precursors constitute less than 50% of bone marrow nucleated cells, the percentage of blasts is based on all nucleated cells; when there are 50% or more erythroid cells, the percentage blasts should be based on the nonerythroid cells. The presence of mild megaloblastoid changes may be permitted if they are thought to be consistent with treatment effect. However, persistence of pretreatment abnormalities (eg, pseudo-Pelger-Huet cells, ringed sideroblasts, dysplastic megakaryocytes) are not consistent with CR. In addition, ANC $> 1000/\mu\text{l}$ and platelet count of $\geq 100,000/\mu\text{l}$. Patient must be independent of transfusions. No duration requirement for this designation.

Cytogenetic complete remission (CCR) – Defined as morphologic complete remission plus a reversion to a normal karyotype. For this study, reversion of a normal karyotype is defined as no clonal abnormalities detected in a minimum of 20 mitotic cells.

Morphologic complete remission with incomplete blood count recovery (CRi) – Defined as morphologic complete recovery with the exception of neutropenia $< 1000/\mu\text{l}$ or thrombocytopenia $< 100,000/\mu\text{l}$.

Partial remission (PR) – Defined as meeting the above criteria for complete remission, with the following exceptions: decrease of $\geq 50\%$ in the percentage of blast to 5-25% in the bone marrow aspirate. A value of $\leq 5\%$ blasts in bone marrow with Auer rods present may also be considered a partial remission.

Stable Disease (SD) – Defined as not meeting the definitions of CR, CRi, PR, PD, or recurrence/morphologic relapse.

Progressive disease (PD) – Defined as a clear increase in bone marrow blast count, typically a greater than 50% increase compared with baseline, or new extramedullary disease. Patients with a $> 50\%$ increase in peripheral blast count with an increase of the total peripheral white blood cell count to $> 10,000/\mu\text{l}$ should undergo evaluation by bone marrow biopsy to access for progressive disease.

Recurrence/morphologic relapse - Defined as relapse following complete remission is defined as reappearance of blasts in the blood or the finding of $\geq 5\%$ blasts in the bone marrow, not attributable to any other cause. New dysplastic changes is considered relapse.

If there are no blasts in the peripheral blood and 5-20% blasts in the bone marrow, bone marrow biopsy should be repeated in > 1 week to confirm relapse.

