We and others have recently used whole genome sequencing to identify recurrent, somatic mutations in AML and MDS patients in four genes that are involved in methylcytosine regulation: *DNMT3A*, *IDH1*, *IDH2*, and *TET2*. [29-37] Collectively, nearly half of all AML/MDS patients have a mutation in one of these four genes. *DNMT3A* mutations are associated with an adverse outcome in AML patients treated with cytotoxic chemotherapy. [35, 38] However, it is not yet clear whether the presence of mutations in one or more of these genes is associated with response or resistance to decitabine.

In this study, we will treat patients with the current state-of-the-art decitabine schedule. [3] We will perform exome sequencing on all patients and correlate response with mutation status, rate of mutation clearance, expression profile, plasma decitabine levels, and DNA

methylcytosine content reduction. This approach will comprehensively assess genomic and pharmacologic parameters that could clinically predict patient response to decitabine.

In this study, we will combine analysis of patients with AML and MDS. Recent genomic analysis has shown that AML and MDS have shared mutations in many of the same genes, shared patterns of mutation acquisition, and shared patterns of mutation evolution.[39, 40] Furthermore, MDS, like AML, presents with clonal hematopoiesis, even when the morphologic blast count is zero.[36] Because this study will identify and track the rate of clearance of patient specific mutations, and because decitabine has been shown to have efficacy in both AML and MDS patients, [2, 3, 16-19, 41-45] combining analysis of AML and MDS patients is reasonable. Asymptomatic MDS patients are excluded because these patients are typically followed with watchful-waiting rather than with chemotherapy.

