9.2 Response Criteria - MDS

MDS Patients will be assessed for response according to the IWG criteria:⁶⁹

Complete remission (CR) – Defined as $\leq 5\%$ myeloblasts with normal maturation of all cell lines in the bone marrow and peripheral blood values of Hgb ≥ 11 g/dL, Platelets $\geq 100 \times 10^9/L$, Neutrophils $\geq 1.0 \times 10^9/L$, and 0% blasts. Persistent dysplasia does not exclude CR but will be noted.

Marrow Complete Response (Marrow CR) – Defined as $\leq 5\%$ myeloblasts in the bone marrow and a decrease by $\geq 50\%$ from pretreatment values, but not meeting the definition of CR above.

Partial Remission (PR) – Defined as meeting the definition of CR above with a decrease of myeloblasts in the bone marrow by $\geq 50\%$ from pretreatment values, but absolute myeloblasts still $>5\%$.

Stable Disease (SD) – Defined as not meeting the definitions of CR, Marrow CR, PR, SD, PD, or recurrence/morphologic relapse.

Progressive Disease//Relapse (PD) – Defined as $\geq 50\%$ increase in blasts to $> 5\%$ blasts (for patients with less than 5% blasts at baseline only), $\geq 50\%$ increase to $> 10\%$ blasts (for patients with 5-10% blasts at baseline only), $\geq 50\%$ increase to $> 20\%$ blasts (for patients with 10-20% blasts at baseline only), $\geq 50\%$ increase to $> 30\%$ blasts (for patients with 20-30% blasts at baseline only) or any of the following: At least 50% decrement from maximum remission/response in granulocytes or platelets, reduction in Hgb by ≥ 2 g/dL, or New or worsened transfusion dependence not related to study drug toxicity. Or for patients with a CR, Marrow CR, or PR as defined above and subsequently development of one of the following: Return to pretreatment bone marrow blast percentage, decrement of $\geq 50\%$ from maximum remission/response levels in granulocytes or platelets, or reduction in Hgb concentration by ≥ 1.5 g/dL or transfusion dependence.

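### Sections 9.1 and 9.2 define response differently for AML and MDS, but the primary gene-response test pools the two diseases without stratifying by diagnosis

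*Combined protocol and SAP*

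**What the plan says.** Section 1.1 announces the pooling: "In this study, we will combine analysis of patients with AML and MDS". It argues from shared mutations and from decitabine activity in both diseases, and does not discuss response criteria.

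Section 9.1 (AML) holds that "persistence of pretreatment abnormalities (eg, pseudo-Pelger-Huet cells, ringed sideroblasts, dysplastic megakaryocytes) are not consistent with CR". CRi is "Defined as morphologic complete recovery with the exception of neutropenia" or low platelets, so it relaxes blood counts only. PR is "Defined as meeting the above criteria for complete remission, with the following exceptions": blasts at least halved, to 5-25%. Below that range the only route is that "blasts in bone marrow with Auer rods present may also be considered a partial remission". Stable disease is what remains: "Defined as not meeting the definitions of CR, CRi, PR, PD, or recurrence/morphologic relapse".

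Section 9.2 (MDS) asks for marrow blasts of at most 5% "with normal maturation of all cell lines in the bone marrow and peripheral blood values of Hgb" of at least 11 g/dL, with platelet and neutrophil limits and no blood blasts. It then adds: "Persistent dysplasia does not exclude CR but will be noted". A cleared marrow (blasts at most 5% and at least halved) that misses CR is Marrow CR.

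Section 14.2.2 tests each mutation against overall response in AML and MDS together, using contingency tables with a chi-square or Fisher test. It also plans a logistic model for unspecified demographic and clinical characteristics, and a permutation of response status. It does not define overall response. Section 14.2.3 gives the overall set as CR/CRi/PR. The subgroups in Section 14.2.5 are age, cytogenetics and mutation status, not diagnosis.

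**The concern.** Each disease follows its own cited IWG criteria, so neither section is wrong alone. The difficulty comes from putting both into one responder variable. Whether the same remission counts as a response then depends partly on the diagnosis. If a gene is also commoner in one disease, diagnosis is linked to both sides of the contingency table and can produce an association where the gene has no effect. The study is meant to decide whether any mutation warrants testing before treatment, so a signal that only reflects the AML/MDS mix would be misread.

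**Working it through.** **1. Classification.** Three patients, each with blasts below 5% (at least halved from baseline), no Auer rods, no extramedullary disease, no blood blasts and no transfusions:

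| Patient | Under 9.1 (AML) | Under 9.2 (MDS) |
|---|---|---|
| A. Hgb, platelets and neutrophils recovered; persistent pretreatment dysplasia | Not CR (dysplasia). Not CRi (only counts relaxed). Not PR (blasts too low, no Auer rods). Stable disease: non-responder | CR: responder |
| B. No dysplasia, low neutrophils or platelets | CRi: responder | Marrow CR: not in CR/CRi/PR |
| C. No dysplasia, neutrophils and platelets recovered, Hgb below 11 | CR (no Hgb limit): responder | Marrow CR: not in CR/CRi/PR |

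A lowers the AML response rate relative to MDS. B and C lower the MDS rate relative to AML. The AML bar concerns pretreatment abnormalities only; mild megaloblastoid change is allowed.

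**2. The plan's own figure.** Section 14.2.2 states 80% power for N = 100, 20% mutated, overall CR/CRi 45%, a 30-point difference and two-sided alpha 0.10.
- Rates: wild type 0.45 - 0.20 x 0.30 = 0.39; mutant 0.69.
- Null SE = sqrt[0.45 x 0.55 x (1/20 + 1/80)] = 0.1244.
- Alternative SE = sqrt(0.69 x 0.31/20 + 0.39 x 0.61/80) = 0.1169.
- Power = Phi[(0.30 - 1.645 x 0.1244)/0.1169] = Phi(0.816) = 79.3%. The figure reproduces.

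**3. False association for a gene with no effect.** The documents give neither the AML share nor any dysplasia rate. Assumed: 70% AML; gene frequency 15% in AML and 30% in MDS (the ends of the range in 14.2.2); 45% response before the bar in both diseases; 30% of AML remissions lost to dysplasia, so the AML rate is 0.45 x 0.70 = 0.315.
- Mutated overall: 0.7 x 0.15 + 0.3 x 0.30 = 0.195.
- Response in mutated: (0.105 x 0.315 + 0.090 x 0.45)/0.195 = 0.377.
- Response in wild type: (0.595 x 0.315 + 0.210 x 0.45)/0.805 = 0.350.
- False difference: 2.7 points.
- Type I error at nominal two-sided 5%, N = 100: null SE 0.1208, alternative SE 0.1220. Upper tail beyond (1.96 x 0.1208 - 0.0271)/0.1220 = 1.72, lower tail beyond 2.16; together 5.8%. A simulation of 200,000 trials gives 6.0%.

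With AML at 50-70%, dysplasia at 10-30%, and frequencies of 15% and 30% assigned either way, the difference is 0.7 to 2.9 points in absolute value and the type I error 5.0% to 5.9%.

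**4. Direction.** Keep the step 3 inputs, but also let 30% of would-be MDS responders be uncounted Marrow CR. Both rates are then 0.315, the false difference is 0.0 and the type I error 5.0%. Now lift only the AML bar (AML 0.45, MDS 0.315):
- Mutated: (0.105 x 0.45 + 0.090 x 0.315)/0.195 = 0.388.
- Wild type: (0.595 x 0.45 + 0.210 x 0.315)/0.805 = 0.415.
- False difference: -2.7 points; type I error 5.4%.

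**5. Stratifying.** In simulation of the scenarios in steps 3 and 4, a Cochran-Mantel-Haenszel test stratified by diagnosis rejects in 4.9-5.0% of trials.

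**The case against.** The strongest defence is that disease-specific IWG criteria are the accepted way to score each disease, that pooling is argued openly in Section 1.1, and that AML versus MDS is a clinical characteristic the logistic model could adjust for. The first two parts stand, and they are a reason to leave Sections 9.1 and 9.2 alone. The third stands only in part: the model names no covariates, and the contingency-table test is unadjusted.

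A reader might infer a serious loss of power from the dysplasia bar. If 45% were the rate before the bar, 70% AML and 30% dysplasia would shrink the 30-point difference to 0.30 x (1 - 0.7 x 0.3) = 23.7 points, and power would fall from 79% to 63%. The documents do not support that reading. The 45% is stated as a CR/CRi rate, and Section 9.1 defines those categories with the bar in place for AML. If the planned rate already reflects this, nothing is lost against plan.

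A reader might also infer that AML is the disadvantaged group and that relaxing the AML rule would cure the problem. Patients B and C, and step 4, show why this does not follow: with Marrow CR uncounted, removing only the AML bar can create an imbalance that was not there.

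**Conclusion.** The point holds as an analysis gap. Response is defined by diagnosis in at least two opposing ways, the primary test ignores diagnosis, and no section reconciles the two. A gene that differs in frequency between AML and MDS can show a spurious association of unknown direction. On the inputs assumed here it is about 3 points, with a type I error near 6% against a nominal 5%. That depends on an AML share and a dysplasia rate which the documents do not give, and it vanishes if the gene is equally common in both diseases or the two asymmetries cancel. The case for change rests on the low cost of removing the ambiguity, not on a large bias.

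**What to change.** In Section 14.2.2:
- Make the primary gene-response test stratified by AML/MDS (Cochran-Mantel-Haenszel, or an exact stratified test where counts are small).
- Permute response status within diagnosis when deriving the empirical P value.
- Name diagnosis as a covariate in the logistic model.
- State whether MDS Marrow CR counts as overall response.

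Keep the 9.1 and 9.2 categories as written. Add one sensitivity analysis with a harmonised response, in which AML patients who miss CR or CRi only because of persistent dysplasia count as responders, and show it beside the main result.

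The cost is a few lines in Section 14 and a negligible loss of efficiency from two strata. Diagnosis is already recorded and marrow morphology is already assessed at the scheduled biopsies, so no new procedure is needed.

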9.2 Response Criteria - MDS

MDS Patients will be assessed for response according to the IWG criteria:⁶⁹

Complete remission (CR) – Defined as $\leq 5\%$ myeloblasts with normal maturation of all cell lines in the bone marrow and peripheral blood values of Hgb ≥ 11 g/dL, Platelets $\geq 100 \times 10^9/L$, Neutrophils $\geq 1.0 \times 10^9/L$, and 0% blasts. Persistent dysplasia does not exclude CR but will be noted.

Marrow Complete Response (Marrow CR) – Defined as $\leq 5\%$ myeloblasts in the bone marrow and a decrease by $\geq 50\%$ from pretreatment values, but not meeting the definition of CR above.

Partial Remission (PR) – Defined as meeting the definition of CR above with a decrease of myeloblasts in the bone marrow by $\geq 50\%$ from pretreatment values, but absolute myeloblasts still $>5\%$.

Stable Disease (SD) – Defined as not meeting the definitions of CR, Marrow CR, PR, SD, PD, or recurrence/morphologic relapse.

Progressive Disease//Relapse (PD) – Defined as $\geq 50\%$ increase in blasts to $> 5\%$ blasts (for patients with less than 5% blasts at baseline only), $\geq 50\%$ increase to $> 10\%$ blasts (for patients with 5-10% blasts at baseline only), $\geq 50\%$ increase to $> 20\%$ blasts (for patients with 10-20% blasts at baseline only), $\geq 50\%$ increase to $> 30\%$ blasts (for patients with 20-30% blasts at baseline only) or any of the following: At least 50% decrement from maximum remission/response in granulocytes or platelets, reduction in Hgb by ≥ 2 g/dL, or New or worsened transfusion dependence not related to study drug toxicity. Or for patients with a CR, Marrow CR, or PR as defined above and subsequently development of one of the following: Return to pretreatment bone marrow blast percentage, decrement of $\geq 50\%$ from maximum remission/response levels in granulocytes or platelets, or reduction in Hgb concentration by ≥ 1.5 g/dL or transfusion dependence.

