5.0 INVESTIGATIONAL PLAN

5.1 Summary of Study Design

This is an open-label, single-arm, Phase II, biomarker study of patients with AML or MDS who are treated with 10 consecutive days of decitabine. FAB-M3 AML is excluded from this trial, because other well-tolerated options exist for the treatment of FAB-M3 acute promyelocytic leukemia. AML patients who are < 60 years old and have not received cytotoxic induction chemotherapy are also excluded, because cytotoxic therapy offers a curative possibility for these patients. MDS patients without cytopenias are also excluded because these patients can be followed with watchful-waiting.

All patients will undergo bone marrow biopsies pre-study, on Cycle 1 Day 10 \pm 1, and on Day 28 \pm 4 of Cycles 1, 2, 4, and 6. Following Cycle 6, bone marrow biopsies should be performed at the discretion of the treating physician to assess for relapse or progression. Patients will provide a skin biopsy sample pre-study. See Section 8.0 for details on correlative studies.

Patients will receive decitabine 20 mg/m²/day as a 1-hour infusion on consecutive Days 1-10 in 28-day cycles. The dose will be calculated based on actual patient weight at the beginning of each cycle.

Once AML patients achieve morphologic complete remission with incomplete blood count recovery (CRi) or MDS patients achieve a marrow complete response (Marrow CR) as defined in Section 9.0, decitabine administration may be decreased to 20 mg/m²/day for ten consecutive days every 6 weeks, to limit myelosuppressive toxicity and improve count recovery. After 2 cycles at 6 week intervals, the dose may be reduce to 20 mg/m²/day for five consecutive days in 6 week cycles, at the discretion of the treating physician. After two cycles of five consecutive days of treatment, if the patient meets the definition of CR with complete cytogenetic response as defined in Section 9.0, administration may further be decreased to three consecutive days per cycle at the discretion of the treating physician.

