5.3 Duration of Therapy

If at any time the constraints of this protocol are considered to be detrimental to the patient's health and/or the patient no longer wishes to continue protocol therapy, the protocol therapy should be discontinued and the reason(s) for discontinuation documented in the case report forms.

In the absence of treatment delays due to adverse events, treatment may continue indefinitely or until one of the following criteria applies:

- Documented and confirmed disease progression
- Death
- Adverse event(s) that, in the judgment of the investigator, may cause severe or permanent harm or which rule out continuation of study drug
- General or specific changes in the patient's condition render the patient unacceptable for further treatment in the judgment of the investigator
- Suspected pregnancy
- Serious non-compliance with the study protocol
- Lost to follow-up
- Patient withdraws consent
- Investigator removes the patient from study
- The Siteman Cancer Center decides to close the study

Patients who prematurely discontinue treatment for any reason will be followed as indicated in the study calendar.

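### In MDS responders, a decitabine count nadir that reaches a trigger counts as relapse as Section 9.2 is written, because that sentence has no cause exclusion and no confirmation

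*Combined protocol and SAP*

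**What the plan says.** Section 9.2 puts MDS progression and relapse in one entry made of two sentences. The first covers blast increases, falls in granulocytes, platelets or Hgb, and transfusion need, and ends with "New or worsened transfusion dependence not related to study drug toxicity". The second opens "Or for patients with a CR, Marrow CR, or PR as defined above and subsequently development of one of the following". Any one of four findings then suffices:

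- marrow blasts back at the pretreatment percentage;
- a fall of at least 50% "from maximum remission/response levels in granulocytes or platelets, or reduction in Hgb concentration by" at least 1.5 g/dL (two findings, counts and Hgb);
- transfusion dependence.

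The text is the same in all five protocol copies in the combined document.

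AML relapse in 9.1 is framed differently. It is "reappearance of blasts in the blood or the finding of" at least 5% marrow blasts, provided no other cause explains it; new dysplasia also counts. With no blood blasts and 5-20% marrow blasts, "bone marrow biopsy should be repeated in > 1 week to confirm relapse".

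The plan expects myelosuppression in responders. Section 5.1 lets them move to ten-day courses "every 6 weeks, to limit myelosuppressive toxicity and improve count recovery". Section 6.1 gives four cycles without adjustment for cytopenia. CBCs are weekly, or every other week after Cycle 1 at the physician's discretion (5.2.6), with a further CBC on Day 1 of each cycle (5.2.3).

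**The concern.** MDS relapse is judged partly on the same counts that the study drug suppresses, in patients who are still being dosed. Read literally, one low CBC between cycles turns a continuing marrow remission into relapse or progression. The plan guards against another explanation for AML relapse but not here, where the risk is greater.

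An investigator may well discount a nadir, but no text says how. With at least three centers planned (14.3) and CBC frequency discretionary, both detection and classification would vary by site.

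These outputs depend on the definition:

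- the per-patient time to relapse (14.2.3);
- time to disease progression, which 1.3 correlates with the velocity and depth of mutation clearance;
- hematologic improvement and cytogenetic response, both nullified by progression (9.2.1, 9.3.1);
- if 9.4 takes its recurrence event from this entry, event-free survival, duration of CR and relapse-free survival.

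**Working it through.** The plan states no figure on this point, so there is none to reproduce. The check is a reading of the definition plus arithmetic on its thresholds.

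**Scope of the exclusion.** The toxicity phrase closes the first sentence and by position qualifies transfusion dependence. The responder sentence starts afresh and lists its own findings. Grammar does not carry the exclusion forward. Even in the first sentence it does not reach the falls in granulocytes, platelets or Hgb.

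**Side by side.**

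| Feature | AML relapse (9.1) | MDS relapse in responders (9.2) |
|---|---|---|
| Based on | Blasts or new dysplasia | Blasts, counts, Hgb or transfusion |
| Other causes excluded | Yes, for the blast criteria | No |
| Confirmation | Repeat marrow in the 5-20% case | None |

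**Trigger levels.** Inputs are the 9.2 CR thresholds (Hgb 11 g/dL, platelets 100 and neutrophils 1.0 ×10⁹/L) and the relapse rule: best value × 0.5 for counts, best value − 1.5 for Hgb.

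| Best value in response | Relapse trigger | CR threshold |
|---|---|---|
| Platelets 100 | 100 × 0.5 = 50 | 100 |
| ANC 1.0 | 1.0 × 0.5 = 0.5 | 1.0 |
| Hgb 11.0 | 11.0 − 1.5 = 9.5 | 11 |
| Platelets 200 | 200 × 0.5 = 100 | 100 |
| ANC 2.0 | 2.0 × 0.5 = 1.0 | 1.0 |
| Hgb 12.5 | 12.5 − 1.5 = 11.0 | 11 |

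In the last three rows the same CBC satisfies the CR count criteria and the relapse rule.

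**Effect on one date, given a nadir that reaches a trigger.** Take CR documented at Cycle 2 Day 28 (day 56) and 28-day cycles. Weekly Cycle 3 CBCs fall on days 63, 70, 77 and 84, so recorded remission is 63 − 56 = 7 to 84 − 56 = 28 days. If the Cycle 4 Day 28 marrow (day 112) still shows CR, remission has lasted at least 112 − 56 = 56 days. The record is then short by at least 56 − 28 = 28 to 56 − 7 = 49 days.

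**How often.** The documents give no rate for such nadirs. As an assumption, let q be the chance per cycle, independent across cycles. The chance of at least one false relapse over k remission cycles is 1 − (1 − q)^k:

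| q | k = 2 | k = 4 |
|---|---|---|
| 10% | 19% | 34% |
| 30% | 51% | 76% |
| 50% | 75% | 94% |
| 70% | 91% | 99% |

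The range is too wide to serve as an estimate. It shows only that repeated cycles accumulate the risk.

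**The case against.** The strongest reply concerns reach.

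**The link to 9.4.** Those endpoints end at recurrence, a term defined only in 9.1 for AML. The MDS stable-disease entry lists PD and recurrence/morphologic relapse as separate items, which suggests they differ. This stands: the link is an inference. It remains the natural one, because 9.2 offers no other MDS relapse definition; without it, MDS patients have no defined recurrence event.

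**Planned analyses.** Section 14 specifies no analysis of event-free survival, CR duration or relapse-free survival; it only lists time to relapse. This stands and limits the consequence.

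**Stopping treatment.** A reader might infer that responders would be taken off drug at a nadir. The documents do not support that. Section 5.3 requires "Documented and confirmed disease progression", 6.1 continues dosing through cytopenia to Cycle 4, and the study schema describes removal for progression after two cycles by marrow blasts. However, 5.3 does not define confirmation, and none of these provisions changes a 9.2 classification or its date.

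**The outside criteria.** Section 9.2 cites the IWG criteria, which may contain an exclusion. The documents do not reproduce them, and the rule as written for responders has none.

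**Conclusion.** The defect holds as a matter of text: an MDS responder whose decitabine nadir reaches a trigger has relapse/PD under 9.2. Smaller nadirs do not qualify. It can misdate the listed time to relapse and the time-to-progression correlate, and can nullify hematologic improvement and cytogenetic response. The effect on event-free survival, CR duration and relapse-free survival rests on reading recurrence in 9.4 as the MDS entry.

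Two stronger readings should be resisted. One is that the main result is compromised. Nothing in the plan lets a later relapse cancel a response already achieved, so the primary comparison is untouched, as are overall survival, power and sample size. The other is a count of affected patients, obtained by applying the planned 45% CR/CRi rate to some share of the 125. The MDS share is not stated, the 45% is for the combined cohort, the MDS criteria have no CRi category, and the nadir rate is unknown. No such number can be derived.

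This is worth an amendment because the rule itself misclassifies an expected drug effect and the correction is cheap.

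**What to change.** Amend 9.2, in both sentences:

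1. Count a fall in granulocytes, platelets or Hgb, or transfusion dependence, only if it is not attributable to decitabine, infection, bleeding or another cause.
2. Require also that it is still present at the next pre-dose Day 1 CBC (already scheduled in 5.2.3), or that the next scheduled marrow no longer meets the response.
3. Once confirmed, date the event to the first qualifying CBC.
4. A return to the pretreatment blast percentage needs no count confirmation.

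In 9.4, state that recurrence for MDS means relapse as defined in 9.2.

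A longer drug-free test, such as persistence to six weeks after the last dose, would not work. On schedule, the next dose comes 29 − 10 = 19 days after the last in a 28-day cycle, and 43 − 10 = 33, 43 − 5 = 38 or 43 − 3 = 40 days after it in a 42-day cycle with ten, five or three dosing days. All are under 42. Because counts may still be low at 19 days, the attribution clause is needed alongside the repeat CBC.

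The cost is an amendment to the wording. Confirmation uses CBCs and marrows already scheduled, with no extra procedures. The downside is that a true count-only relapse is confirmed up to one cycle later, although it is dated back. A persistent, unexplained halving from a high peak would still count as relapse within the CR thresholds; whether it should is a clinical choice.
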